18.3. Analysis of Efficacy

This study is not intended to assess efficacy, but rather the IGA is included to determine the need for treatment and subsequent re-treatment after treatment course (in either Study SGT-54-01 or Study SGT-54-02 or for new patients not previously enrolled in Study SGT-54-01 or Study SGT-54-02) and any subsequent 4-week courses, if applicable. Certain efficacy data and endpoints will, however, be summarized.

Descriptive statistics will be used to summarize the assessment of efficacy. IGA scores will be summarized at Baseline Visit of Study SGT-54-01 or Study SGT-54-02 or at the Screening visit of SGT-54-07 for those patients not previously enrolled in Study SGT-54-01 or Study SGT-54-02, and entry into the study (SGT-54-07) and every 4 weeks through end of the study. The number and percentage of patients who achieve treatment success at the scheduled study visits will be tabulated.

The number of retreatments is defined as the number of clinical confirmations of the condition for which the subject was initially treated after the first treatment period with S5G4T-1. For rollover subjects previously treated with Vehicle Cream, this is the number after the initial treatment in Study SGT-54-07. For rollover subjects previously treated with S5G4T-1, this is the number of treatments in Study SGT-54-07 following the cessation of the treatment which began in Study SGT-54-01 or Study SGT-54-02.

The number of treatment free days until the first retreatment (relapse) will be calculated and analyzed. For rollover subjects previously treated with Vehicle Cream, the number of treatment free days will be the number of days between the end of the initial treatment in study SGT-54-07 and the start of the next treatment in study SGT-54-07 if one should be needed or the end of the subject's participation in study SGT-54-07. For rollover subjects previously treated with S5G4T1, the number of treatment free days will be the of days between the end of the initial treatment that began in Study SGT-54-01 or Study SGT-54-02 and the start of the next treatment in study SGT-54-07 if one should be needed or the end of the subject's participation in the study SGT-54-07.

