8.1.3 Visit Windowing

For subjects receiving S5G4T-1 in 54-01/54-02, data from 54-01/54-02 will be included in summaries of 54-07. For subjects receiving vehicle in 54-01/54-02, baseline values will be sourced from 54-01/54-02 and data from follow-up visits of 54-07 will be used in summaries. The table below details the analysis visits to be summarized and the associated visits from 54-01/54-02 or 54-07 which will be sourced for each type of subject.

Analysis Visits for Efficacy and Safety Assessments

Analysis Visit	Subjects Receiving S5G4T-1 in 54-01/54-02	Subjects Receiving vehicle in 54-01/54-02
Week 4	54-01/02 - Week 4	54-07 - Week 4
Week 8	54-01/02 - Week 8	54-07 - Week 8
Week 12	54-01/02 - Week 12	54-07 - Week 12
Week 16	54-07 - Week 4	54-07 - Week 16
Week 20	54-07 - Week 8	54-07 - Week 20
Week 24	54-07 - Week 12	54-07 - Week 24
Week 28	54-07 - Week 16	54-07 - Week 28
Week 32	54-07 - Week 20	54-07 - Week 32
Week 36	54-07 - Week 24	54-07 - Week 36
Week 40	54-07 - Week 28	54-07 - Week 40
Week 44	54-07 - Week 32	Not available
Week 48	54-07 - Week 36	Not available
Week 52	54-07 - Week 40	Not available

Data from 54-07 will be mapped to the appropriate analysis visit described above based on nominal visit indications. Data from Early Termination (ET) and unscheduled visits will be determined using analysis visit windows. The analysis visit windows for ET and unscheduled visits are presented in the following table.

SGT-54-07 Analysis Visit Windows for Efficacy and Safety Assessments

Nominal Visit	Target Study Day¹	Window (Days)
Week 4	29	22 to 42
Week 8	57	43 to 70
Week 12	85	71 to 98
Week 16	113	99 to 126
Week 20	141	127 to 154
Week 24	169	155 to 182
Week 28	197	183 to 210
Week 32	225	211 to 238
Week 36	253	239 to 266
Week 40	281	267 to 294
Week 44	309	295 to 322
Week 48	337	323 to 350
Week 52	365	351 to 378

¹ Number of days since nominal Baseline visit of 54-07

Data collected at ET and unscheduled visits prior to study day 22 will not be analyzed. Data collected at ET and unscheduled visits after study day 378 will not be included in analyses.

The definition for the study day included in each study window is defined as below:

Study Day prior to Day 1 = Visit Date – Day 1 Date

Study Day on or after Day 1 = Visit Date – Day 1 Date + 1

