8.8.2 Retreatments

The number of retreatments is defined as the number of clinical confirmations of the condition for which the subject was initially treated after the first treatment period with S5G4T-1. For rollover subjects previously treated with vehicle, this is the number of treatments after the initial treatment in 54-07. For rollover subjects previously treated with S5G4T-1, this is the number of treatments in 54-07 following the cessation of the treatment which began in 54-01 or 54-02. A clinical confirmation of the condition will be defined as IGA no longer being clear or almost clear after a previous IGA of clear or almost clear. When a subject has a clear or almost clear IGA in 54-07, it is expected they were instructed not to dose until the IGA reached mild, moderate or severe.

The number of treatment free days until the first retreatment (relapse) will be calculated and summarized. Relapse will be defined as a subject no longer having an IGA of clear or almost clear after a previous visit IGA of clear or almost clear. When a subject has a clear or almost clear IGA in 54-07, it is expected they were instructed not to dose until the IGA reached mild, moderate or severe. Number of treatment free days until first retreatment is defined as the number of days between an initial IGA assessment of clear or almost clear while the subject was receiving S5G4T-1 until an IGA of mild, moderate or severe.

For rollover subjects previously treated with vehicle, the number of treatment free days will be the number of days between the end of their first treatment of S5G4T-1 in 54-07 (when the subject has an IGA of clear or almost clear) and the start of the next treatment in 54-07 (when the

subject has an IGA indicating they should dose) if they treated with S5G4T-1 again or the end of the subject's participation in 54-07. For rollover subjects previously treated with S5G4T-1, the number of treatment free days will be the number of days between the end of the treatment that began in 54-01 or 54-02 (when the subject has an IGA of clear or almost clear) and the start of the next treatment in 54-07 (when the subject has an IGA indicating they should dose) if they treated with S5G4T-1 again or the end of the subject's participation in the 54-07.

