3 - Severe	xx (xx.x%)	xx (xx.x%)	xx (xx.x%)
Week 44^b			
n	xx	NA	xx
0 - None	xx (xx.x%)		xx (xx.x%)
1 - Mild	xx (xx.x%)		xx (xx.x%)
2 - Moderate	xx (xx.x%)		xx (xx.x%)
3 - Severe	xx (xx.x%)		xx (xx.x%)

^a Baseline is defined as the baseline value from SGT-54-01/SGT-54-02.

^b Table summaries based analysis visits, representing time from first dose of E-BPO 5% Cream.

SOURCE: USERNAME\SPONSOR\PROJECT\JOBNAME (DATE,TIME)

Table 14.2.4: Summary of Telangiectasia Assessment at Each Evaluation
(Safety Population)
(Page 5 of 5)

Telangiectasia Assessment	SGT-54-01/SGT-54-02 Vehicle Cream (N=xxx)	SGT-54-01/SG-54-02 E-BPO 5% Cream (N=xxx)	SGT-54-07 E-BPO 5% Cream (N=xxx)
Week 48 ^b			
n	xx	NA	xx
0 - None	xx (xx.x%)		xx (xx.x%)
1 - Mild	xx (xx.x%)		xx (xx.x%)
2 - Moderate	xx (xx.x%)		xx (xx.x%)
3 - Severe	xx (xx.x%)		xx (xx.x%)
Week 52 ^b			
n	xx	NA	xx
0 - None	xx (xx.x%)		xx (xx.x%)
1 - Mild	xx (xx.x%)		xx (xx.x%)
2 - Moderate	xx (xx.x%)		xx (xx.x%)
3 - Severe	xx (xx.x%)		xx (xx.x%)

^a Baseline is defined as the baseline value from SGT-54-01/SGT-54-02.

^b Table summaries based analysis visits, representing time from first dose of E-BPO 5% Cream.

SOURCE: USERNAME\SPONSOR\PROJECT\JOBNAME (DATE,TIME)

Table 14.2.5: Summary of Reoccurrence
(Safety Population)

	E-BPO 5% Cream (N=xxx)
Number of Retreatments	
n	xx
Mean	xx.x
SD	xx.xx
Median	xx.x
Min. to Max.	xx to xx
Number of Treatment Free Days Until First Retreatment	
n	xx
Median ^c (days)	xx.x
95% Confidence Interval ^c	(xx.x, xx.x)

^a Number of retreatments is defined as the number of times a subject's IGA goes from clear or almost clear to mild, moderate or severe after the subject was clear or almost clear while receiving E-BPO 5% Cream.

^b Number of treatment free days until first retreatment is defined as the number of days between an initial IGA assessment of clear or almost clear while the subject was receiving E-BPO 5% Cream until an IGA of mild, moderate or severe.

^c Median and 95% confidence intervals based on Kaplan-Meier method.

SOURCE: USERNAME\SPONSOR\PROJECT\JOBNAME (DATE,TIME)

Table 14.3.0.1: Summary of Extent of Exposure
(Safety Population)
(Page 1 of 2)

	SGT-54-01/SGT-54-02 Vehicle Cream (N=xxx)	SGT-54-01/SG-54-02 E-BPO 5% Cream (N=xxx)	SGT-54-07 E-BPO 5% Cream (N=xxx)
Total Number of Days of Exposure			
n	xx	xx	xx
Mean	xx.x	xx.x	xx.x
SD	xx.xx	xx.xx	xx.xx
Median	xx.x	xx.x	xx.x
Min. to Max.	xx to xx	xx to xx	xx to xx
Total Number of Applications			
n	xx	xx	xx
Mean	xx.x	xx.x	xx.x

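### SAP 8.8.2 gives two conflicting start rules for treatment-free days, and the table footnote carries the one that can count on-drug time

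*SAP*

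**What the plan says.** SAP 8.8.2 has three paragraphs that bear on this.

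- **Paragraph 1 (retreatments).** For patients who had S5G4T-1 in Phase 3, "this is the number of treatments in 54-07 following the cessation of the treatment which began in 54-01 or 54-02".
- **Paragraph 2 (treatment-free days, general definition).** The interval runs from "an initial IGA assessment of clear or almost clear while the subject was receiving S5G4T-1 until an IGA of mild, moderate or severe". Relapse is any loss of clear or almost clear status after an earlier visit with that status. Neither statement requires that dosing has stopped.
- **Paragraph 3 (treatment-free days, rollover patients).** For patients with prior S5G4T-1, "the number of treatment free days will be the number of days between the end of the treatment that began in 54-01 or 54-02" and the start of the next treatment in 54-07.

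Table 14.2.5 is the only planned table that reports these quantities. Footnote b starts the day count at "an initial IGA assessment of clear or almost clear while the subject was receiving E-BPO 5% Cream until an IGA of mild" or worse, which is the paragraph 2 rule. Footnote a defines the number of retreatments as changes from clear or almost clear to mild or worse "after the subject was clear or almost clear while receiving E-BPO 5% Cream". It starts no clock.

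Protocol 18.3 agrees with paragraph 3: the interval lies between "the end of the initial treatment that began in Study SGT-54-01 or Study SGT-54-02 and the start of the next treatment in study SGT-54-07". It defines retreatments as "the number of clinical confirmations of the condition for which the subject was initially treated after the first treatment period with S5G4T-1".

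SAP 8.1.3 adds: "For subjects receiving S5G4T-1 in 54-01/54-02, data from 54-01/54-02 will be included in summaries of 54-07". Its table maps Phase 3 Weeks 4, 8 and 12 to analysis Weeks 4, 8 and 12.

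**The concern.** In 54-07, product is withheld once the IGA is 0 or 1, so the first clear visit and the end of dosing nearly coincide. That is why the two rules give much the same answer for prior-vehicle patients, whose first S5G4T-1 course lies wholly in 54-07. Phase 3 is described as a 12-week treatment period, and SAP 8.8.2 states the instruction to stop at IGA 0 or 1 only for 54-07. A prior S5G4T-1 patient who first cleared at Phase 3 Week 4 or 8 was therefore probably still applying the product.

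Read literally for such a patient, footnote b starts a treatment-free clock on a treatment day. Two things can then go wrong: on-drug remission lengthens the interval, or an on-drug worsening closes it and is recorded as the relapse. Table 14.2.5 reports a Kaplan–Meier median with a 95% confidence interval in one column that pools both kinds of rollover patient. Its meaning would depend on which paragraph the programmer followed.

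**Working it through.** The plan states no figure for treatment-free days, so there is none to reproduce. The check applies both rules to the visit schedule.

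**Inputs**
- Mapped Phase 3 visits: Weeks 4, 8 and 12 (SAP 8.1.3). Nominal day = 7 × week + 1, giving Days 29, 57 and 85.
- End of Phase 3 treatment: Week 12, Day 85, which is also 54-07 Baseline (Protocol 5.1 and 11). The window is ±4 days (Protocol 12.1), so Days 81 to 89.
- Assumption: Phase 3 product was applied through Day 85. The Phase 3 protocols are not among the documents.

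**Rules**
- Rule A (paragraph 2, footnote b): start at the first IGA 0/1 on S5G4T-1; end at the first later IGA 2–4.
- Rule B (paragraph 3, Protocol 18.3): start at the end of the course begun in Phase 3; end when the IGA calls for treatment again.

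**All Phase 3 patterns** (C = IGA 0/1, N = IGA 2–4, at Weeks 4, 8, 12)

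| Pattern | Rule A | Rule B |
|---|---|---|
| CCC | 85 − 29 = 56 on-drug days counted | starts Day 85 |
| NCC | 85 − 57 = 28 on-drug days counted | starts Day 85 |
| NNC | 0 on-drug days | starts Day 85 |
| CCN | relapse on drug after 85 − 29 = 56 days | not started |
| CNC | relapse on drug after 57 − 29 = 28 days | starts Day 85 |
| CNN | relapse on drug after 57 − 29 = 28 days | not started |
| NCN | relapse on drug after 85 − 57 = 28 days | not started |
| NNN | not started | not started |

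Six of the eight patterns start the Rule A clock while drug is still being applied. Two of them add on-drug days and four end in an on-drug relapse. These are counts of possible patterns, not patient frequencies.

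With the Week 12 window and the earlier visit held at its nominal day, 56 becomes 81 − 29 = 52 to 89 − 29 = 60, and 28 becomes 81 − 57 = 24 to 89 − 57 = 32.

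**Example 1.** IGA 1 at Phase 3 Weeks 4, 8 and 12, clear at 54-07 Week 4, IGA 2 at 54-07 Week 8 (Day 85 + 56 = 141). Rule A: 141 − 29 = 112 days. Rule B: 141 − 85 = 56 days.

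**Example 2.** IGA 1, 2, 1 at Phase 3 Weeks 4, 8, 12, clear at 54-07 Weeks 4 and 8, IGA 2 at 54-07 Week 12 (Day 85 + 84 = 169). Rule A: 57 − 29 = 28 days, and footnote a counts 2 retreatments. Rule B: 169 − 85 = 84 days, and paragraph 1 gives 1 retreatment.

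The error is too long in the first example and too short in the second, so no constant corrects it.

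**Limit of the 56-day figure.** The entry criteria refer to Phase 3 Visits 3, 4 and 5 before Week 12, but SAP 8.1.3 maps only Weeks 4 and 8 from that span. The timing of the third visit is not given. If it fell at Week 2 (Day 15, an assumption) and its IGA were used, the figure would be 85 − 15 = 70.

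**The case against.** The best defence is that paragraph 3 is written for exactly these patients, counts no Phase 3 on-drug days and matches the protocol. A specific rule can reasonably be read as applying the general one. The sentence just before the paragraph 2 definition concerns a clear IGA in 54-07 and the instruction not to dose, so the initial assessment could mean the one that stops dosing. On that reading the paragraphs largely agree. Likewise, paragraph 1 already limits retreatments to 54-07, and footnote a may be only a shorthand. Finally, SAP 8.1.3 concerns analysis visits, and Table 14.2.5 lacks the analysis-visit footnote that the by-visit tables carry.

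Much of this stands. A reader might infer that the plan will count Phase 3 on-drug days, or that someone chose to. The documents do not support that, because the correct rule is in the same section.

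The defence does not remove the conflict. Paragraph 2 is phrased as the definition, no sentence gives paragraph 3 precedence, and the table shell carries only the paragraph 2 rule. The opening sentence of SAP 8.1.3 is general and does not exempt this table. Appeal to the protocol is not decisive either: SAP 2 says the SAP prevails where the two differ, and SAP 10 records no change on this point. If paragraph 3 is what is meant, the footnotes still need correcting.

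**Conclusion.** The concern holds as an unresolved conflict between two stated rules, with the table shell carrying the unsuitable one. Programmed literally, footnote b can label 56 or 28 on-drug days as treatment free, or take an on-drug worsening as the relapse, in prior S5G4T-1 patients. Footnote a can add such a worsening to the retreatment count. These sizes assume dosing to Week 12 in Phase 3 and use of the three mapped visits.

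A reader might also infer that the reported median will be too long. That does not follow: the errors run both ways, and the documents do not say how many patients follow each pattern, so the net shift cannot be stated.

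The consequence is limited. One descriptive efficacy table is affected, in a study that is not intended to assess efficacy and has no inferential testing. The adverse event, tolerability and exposure summaries are untouched. It is still worth correcting, because an interval labelled treatment free should contain only time off treatment.

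**What to change.** - **SAP 8.8.2 paragraph 2 and Table 14.2.5 footnote b:** replace the definition with the paragraph 3 rule. Start the interval at the end of the first S5G4T-1 course with IGA 0/1. For patients with prior S5G4T-1, this is no earlier than the end of the course begun in 54-01 or 54-02. If the IGA was still 2–4 at 54-07 Baseline, it is the later end of that course in 54-07.
- **Relapse definition and footnote a:** count only changes from IGA 0/1 to IGA 2–4 that occur after that course has ended.

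A separate row for worsening on drug is not needed.

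The cost is one paragraph and two footnotes, with matching programming, before database lock; SAP 2 allows updates until then. No protocol change is needed, since the result agrees with Protocol 18.3. The last Phase 3 application date and the dosing intervals are already planned for Listings 16.1.7 and 16.2.5.3. If actual last-dose dates are used rather than visit dates, the SAP should say how patients with unknown dosing dates are handled, since they would otherwise drop out of this summary.

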13.2. Screen Failure and Discontinuation Criteria

For new patients, a screen failure is a patient who is not randomized/enrolled in the study due to ineligibility, after signing an Informed Consent Form, and did not receive study product. The Informed Consent Form signed by the patient should be kept with the source document for patients who do not pass the screening procedures. The documentation should include identification of the eligibility criterion or criteria that were and were not met. The patient should not be re-screened for this study without Sol-Gel's approval.

Although encouraged to complete the study whenever possible, patients are free to discontinue their participation in this study at any time and for any reason without prejudice. A patient may be withdrawn from the study prior to study completion for any of the following reasons:

- Investigator opinion that it is not in the patient's best interest to continue.
- Patient Request /Withdraw Consent – Whenever the patient decides it is in his/her best interest to withdraw.
- Adverse Event – when the investigator thinks it's in the patient's best interest
- Lost to Follow-up – Documentation confirmed at minimum by two phone calls and certified letter. Best effort should be performed to capture an explanation for the lost-to follow-up event.
- Protocol Violation – When requirements of the protocol are not respected, especially when patient safety is concerned.
- Pregnancy
- Worsening of condition that requires alternate therapy.

In the event that the Sponsor terminates the study early, every effort will be made to allow patients to complete at least 6 months of treatment.

In the case of patients who discontinue due to an Adverse Event, the Investigator will conduct follow-up contacts with the patient until the Investigator, Sponsor and Medical Monitor agree the event is satisfactorily resolved and/or stabilized.

Patients discontinued early from the study shall not be replaced.

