17.4. Preparation, Dispensing and Storage Instructions

The study product must be dispensed only to study patients and only at study sites specified on the form FDA 1572 by authorized personnel as required by applicable regulations and guidelines.

Study product will be dispensed according to Investigator Global Assessment at: Baseline, Weeks 4, 8, 12, 16, 20, 24, 28, 32 and 36 for patients entering from study SGT-54-01 or study SGT-54-02 and for new patients at: Baseline, Weeks 4, 8, 12, 16, 20, 24, 28, 32, 36, 40, 44 and 48. Study product will be returned at: Weeks 4, 8, 12, 16, 20, 24, 28, 32, 36 and 40 for patients entering from study SGT-54-01 or study SGT-54-02 and for new patients at: Weeks 4, 8, 12, 16, 20, 24, 28, 32, 36, 40, 44, 48 and 52. Study product weight will be documented) prior to dispensing and after return of each pump per flow chart ([Section 13.9](#) and [Section 13.10](#)).

Each Patient will be instructed on the importance of returning his or her study product at each designated visit. If a Patient does not return his or her study product, he or she will be instructed to return it at the next visit.

The study coordinator will question the patient on history of study product use since the last visit and will record any missed doses (as recorded on the patient diary) in both the source documents and the appropriate eCRF. A patient who deviates significantly from the prescribed dosage will be counseled.

Study product should be stored at room temperature 20 to 25°C (68 to 77°F). Excursions permitted between 15 to 30°C (59 to 86°F). Do not freeze or refrigerate the product.

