Descriptive statistics for time to relapse (number of treatment free days until retreatment) and number of retreatments will be presented. A confidence interval (CI) for the median time to relapse will be presented using the Kaplan–Meier method. Patients who discontinue in 54-07 while not being treated and had not yet previously relapsed will be considered censored in the Kaplan–Meier analysis.

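### SAP 8.8.2 ends time to relapse in two conflicting ways, so a relapse first seen at an exit visit may be counted as an event or censored

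*SAP*

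**What the plan says.** **Relapse, by IGA.** SAP 8.8.2: "Relapse will be defined as a subject no longer having an IGA of clear or almost clear", once an earlier visit has shown one of those two grades. The same section's general definition of treatment-free days ends at an IGA of mild, moderate or severe. Footnote b of Table 14.2.5 repeats it.

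**End of interval, by treatment.** The next paragraph of SAP 8.8.2 sets the number of days for each rollover cohort. For former vehicle patients the interval runs to the start of the next treatment, tied to an IGA that calls for dosing, "if they treated with S5G4T-1 again or the end of the" subject's participation. The wording for former S5G4T-1 patients is parallel. The section then treats time to relapse and treatment-free days until retreatment as one quantity.

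**Censoring.** "Patients who discontinue in 54-07 while not being treated and had not yet previously relapsed will be considered censored". This sentence governs the Kaplan-Meier analysis. Completers are not mentioned.

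**Retreatment count.** SAP 8.8.2 starts from clinical confirmations of the condition, defined by IGA, but then describes each cohort's count as a number of treatments. Footnote a of Table 14.2.5 counts each occasion on which "IGA goes from clear or almost clear to mild, moderate or severe after the subject was clear or almost clear while receiving" the cream.

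**Dispensing.** Protocol 17.4, for rollover patients: "Study product will be dispensed according to Investigator Global Assessment at: Baseline, Weeks 4, 8, 12, 16, 20, 24, 28, 32 and 36". The flow chart in Protocol 13.9 shows an IGA but no dispensing at Week 40, and requires all Week 40 procedures of patients who terminate early. The end-of-treatment procedures in 13.15 include no dispensing either.

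**The concern.** A patient who is off product and has an IGA of 2 or more for the first time at an exit visit has relapsed by the IGA definition. That patient cannot start another course in the study, so the treatment-based end can never be reached. If retreatment is what counts as the event, the only other Kaplan-Meier status is censored. Such censoring is informative: the patient leaves the risk set because of the relapse, at the moment it is found.

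Two programmers could each follow SAP 8.8.2 and report different medians. The group need not be small. The sponsor may stop the study once the 28-week and 52-week exposure targets are met (Protocol 11, SAP 6.1), and every patient then on study has an exit visit without dispensing.

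The retreatment count is split in the same way. An IGA rise at the exit visit is a retreatment under footnote a, although no treatment followed.

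**Working it through.** The documents give no relapse rate, median or event count, so there is no planned figure to reproduce. The check sets the rules side by side and then sizes the difference under stated assumptions.

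**Step 1. One patient, two rules.** Take a patient cleared on S5G4T-1, off product, with IGA 0 or 1 at Week 36 and IGA 3 at Week 40.
- IGA rule: event at Week 40.
- Treatment rule: no next treatment, so the interval ends with participation, also at Week 40.
- The number of days is the same. Only event status differs, and no sentence states it for this patient. The censoring sentence names discontinuers only and leaves open whether a relapse found at the exit visit itself counts as having previously occurred.

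**Step 2. Direction.** Kaplan-Meier multiplies factors (1 − e/n), with e events among n at risk. Censoring an exit relapse lowers e and leaves n unchanged at that visit, so no factor falls. The treatment rule cannot shorten estimated remission.

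**Step 3. Size.** From the documents: 4-weekly visits, last visit Week 40, last dispensing Week 36. Assumed, because the documents give no values:
- relapse probability p of 5% to 30% per visit;
- other dropout of 2% per visit;
- a share w (0, 10 or 20%) of relapses before Week 40 where the patient leaves without retreatment;
- clearing at a 54-07 visit: all at Day 1, half at Day 1 and the rest evenly over Weeks 4 to 36, or evenly from Day 1 to Week 36.

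Let t be visits since clearing.

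IGA rule: S(t) = (1 − p)^t for any clearing pattern. At p = 10%, 0.9^6 = 0.531 and 0.9^7 = 0.478, so the median is 7 × 28 = 196 days, and 0.9^10 = 0.349.

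Treatment rule: the hazard at t is p(1 − w)f(t), where f(t) is the share of those at risk at t who are not yet at Week 40.
- All cleared at Day 1, w = 0: f = 1 up to t = 9 and 0 at t = 10. The median stays at 196 days, and only the last step is lost (0.9^9 = 0.387 instead of 0.349). With 0.90 × 0.98 = 0.882 remaining per visit, relapses lost are 0.1 × 0.882^9 = 0.032 of a total of 0.606, or 5.3%.
- Even clearing, w = 0: f(t) = (10 − t)/(11 − t), so the hazards are 0.0900, 0.0889, 0.0875 and so on. S(6) = 0.583, S(8) = 0.504 and S(9) = 0.478, so the median is 9 × 28 = 252 days.

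Results at p = 10% (IGA rule / treatment rule):

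| Clearing pattern | w | Relapses lost | Median, days | Relapse-free 24 weeks after clearing |
|---|---|---|---|---|
| All Day 1 | 0 | 5.3% | 196 / 196 | 53.1% / 53.1% |
| All Day 1 | 20% | 24.3% | 196 / 252 | 53.1% / 60.6% |
| Half Day 1 | 0 | 9.8% | 196 / 224 | 53.1% / 55.5% |
| Even | 0 | 15.4% | 196 / 252 | 53.1% / 58.3% |
| Even | 20% | 32.3% | 196 / not reached | 53.1% / 65.2% |

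Over all p, relapses lost at w = 0 are 1.1 to 7.1% (all Day 1), 6.8 to 11.1% (half) and 12.4 to 16.4% (even). At w = 20% they are 20.9 to 33.1% over all patterns. With all clearing at Day 1 and w = 0, the median did not move at any p tried.

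**Step 4. A second route to the same loss.** SAP 8.1.3 leaves an early-termination or unscheduled value out of analyses when a scheduled visit already fills its window. With a scheduled Week 20 visit on Day 141 and early termination with IGA 3 on Day 150, both fall in the 127 to 154 window. If 8.1.3 is applied to time to relapse, that relapse disappears even under the IGA rule.

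**The case against.** The best defence is that the IGA rule already governs. Relapse is defined by IGA. The cohort paragraphs set a number of days, not event status, and link the next treatment to an IGA that calls for dosing. The only status sentence censors patients who had not relapsed, and both table footnotes use the IGA transition. On that reading an exit-visit relapse is an event and nothing is overstated. A patient who worsens off product may also have an unscheduled visit with dispensing (Protocol 14.1), so many relapses will be retreated. The study is not intended to assess efficacy and does no inferential testing.

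Much of this stands. Censoring is an inference from the text, not a stated rule, and the stakes are limited. The defence does not remove the conflict. SAP 8.8.2 equates relapse with retreatment, and it requires actual treatment where Protocol 18.3 speaks of treatment being needed. The SAP supersedes the protocol (SAP 2) and does not list this among its changes (SAP 10).

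Three stronger readings are tempting and not supported:
- *Table 14.2.5 contradicts itself.* Footnotes a and b use the same IGA transition and agree. The conflict is between the table and the cohort text of 8.8.2.
- *Remission will be overstated.* That follows only if the treatment wording, or the literal censoring wording, sets event status.
- *Withdrawal for worsening is caught between the two rules.* "Worsening of condition that requires alternate therapy" is a listed withdrawal reason in Protocol 13.2, but without an exit IGA of 2 or more it is an event under neither rule. Making it one would create a composite endpoint that neither document defines.

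**Conclusion.** The point holds as a conflict of definition. SAP 8.8.2 allows a relapse first seen at Week 40 or early termination to be either an event or censored, and the retreatment count has a matching split between 8.8.2 and footnote a. If the treatment wording or the literal censoring wording is used, the direction of bias is certain: toward longer remission. The size runs from nil to large. It depends on relapse rates, exit rates and clearing times that the documents do not give, and every figure above rests on assumed values. The effect is confined to one descriptive secondary summary, the Kaplan-Meier median with its interval and the retreatment count. The safety objective is untouched. It is still worth correcting before database lock, because the ambiguity allows patients to be censored because they relapsed.

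**What to change.** In SAP 8.8.2:
1. Delete the condition about being treated again from time to relapse.
2. Define the event as the first IGA of 2 or more after clearance on S5G4T-1, on the date of that assessment, at any visit, including Week 40, early-termination and unscheduled visits. State that the window exclusions in 8.1.3 do not apply to this variable.
3. Censor patients with no such IGA at their last IGA assessment, completers as well as discontinuers.
4. Use one definition for the retreatment count in 8.8.2 and footnote a: either IGA rises or courses restarted, labelled accordingly.

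Counting withdrawals for worsening without an exit IGA of 2 or more as events is optional, and only as a sensitivity analysis.

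The cost is SAP wording and, depending on the choice in item 4, a change to footnote a. The IGA is already collected at these visits, so no new data are needed. The reported remission time may be shorter than the treatment-based wording would have given.
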